Title

Observational Study to Assess the Effectiveness of a Smartphone Application in Enhancing Adoption of the 2024 KDIGO CKD Guideline.

1. Background and Rationale

Chronic Kidney Disease (CKD) affects millions of individuals worldwide, and adherence to clinical guidelines is critical for managing the disease effectively. The 2024 KDIGO CKD Guidelines provide comprehensive recommendations for the diagnosis and management of CKD. However, implementation of these guidelines remains a challenge. This study aims to evaluate the effectiveness of a smartphone application designed to assist doctors and patients in following the 2024 KDIGO CKD guidelines.

2. Objectives

Primary Objective

To assess the effectiveness of a smartphone application in enhancing the adherence to the 2024 KDIGO CKD guidelines over a 18-month period. This includes recommendations on lifestyle modification as well as optimal disease modifying medications to reduce the loss of kidney function and cardiovascular risk over time.

Secondary Objectives

- To evaluate changes in clinical parameters (e.g., blood pressure, eGFR, urinary protein excretion) over the study period.
- To assess patient satisfaction and engagement with the smartphone application.
- To determine the impact of the application on the quality of life of CKD patients.

3. Study Design

This is an observational, prospective cohort study. Participants will be assessed at baseline and at intervals over 18 months.

4. Study Population

Inclusion Criteria

- Adults aged ≥ 16 years.
- Diagnosed with CKD stages 1-5.
- Owns a smartphone and is capable of using mobile applications.
- Provides informed consent.

Exclusion Criteria

- Inability to provide informed consent due to cognitive impairment.

5. Study Procedures

Baseline Visit

1. Obtain informed consent.
2. Collect demographic and medical history.
3. Conduct baseline measurements:
 - Blood pressure
 - Serum creatinine
 - Estimated Glomerular Filtration Rate (eGFR)
 - Urine Albumin-to-Creatinine Ratio (ACR)
 - Weight, height, BMI
4. Collect information on lifestyle factors:
 - Diet
 - Physical activity level
 - Smoking status
 - Alcohol consumption
5. Assist participant in downloading and setting up the smartphone application.

Follow-Up Visits

Participants will be assessed at 3, 6, 9, and 12 months. At each visit:

1. **Collect follow-up measurements:**
 - Blood pressure
 - Serum creatinine
 - eGFR
 - Urine ACR
 - Weight, height, BMI

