2. **Review application usage data:**
 - Number of logins per week
 - Frequency of viewing educational materials
 - Frequency of logging health data
 - Number of reminders received and responded to
3. **Assess adherence to KDIGO guidelines:** *Disease modifying medication*
prescription including ACE inhibitors and ARBs, SGLT2 inhibitors, GLP-1 analogues, Finerenone and endothelial antagonists.
 - *Blood pressure control* versus targets recommended by the KDIGO Guidelines.
 - Dietary recommendations
 - Physical activity recommendations
 - Attendance at medical appointments
4. **Collect patient feedback on the application:**
 - Ease of use (scale 1-5)
 - Usefulness of educational materials (scale 1-5)

- Effectiveness of reminders (scale 1-5)
 - Overall satisfaction (scale 1-5)
 - Suggestions for improvement
5. **Quality of life assessed in patients** using a validated questionnaire (e.g., POS-S-Renal).

6. Outcome Measures

Primary Outcome

- Adherence to the 2024 KDIGO CKD guidelines, measured by changes in adherence scores from baseline to 12 months in the variables specified above (recommended medications and lifestyle modifications).

Secondary Outcomes

- Changes in clinical parameters (blood pressure, serum creatinine, eGFR, urine ACR).
- Patient satisfaction and engagement with the application.
- Quality of life assessed in patients being managed as part of the conservative care pathway using a validated questionnaire (e.g., POS-S-Renal).

7. Data Management and Analysis

Data Collection

Data will be collected using electronic data capture systems. All data will be anonymized and stored securely.

Statistical Analysis

- Descriptive statistics for baseline characteristics and outcome measures.
- Paired t-tests or Wilcoxon signed-rank tests to compare baseline and follow-up measurements.

8. Ethical Considerations

Informed Consent

Written informed consent will be obtained from all participants through the smartphone application.

Confidentiality

Participant confidentiality will be maintained. Data will be anonymized and securely stored.

Ethical Approval

The study protocol has been approved by the hospital ethics committee.

9. Dissemination of Results

The results of the study will be published in peer-reviewed journals and presented at national and international conferences. A summary of the study results will be shared with participants through the smart phone application.

10. Timeline

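### The stated aims are to establish the app's effectiveness and impact, but an uncontrolled before-after comparison can only show that adherence changed among patients given it

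*Protocol*

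**What the plan says.** **Aims.** The primary objective in Section 2 is "To assess the effectiveness of a smartphone application in enhancing the adherence to the 2024 KDIGO CKD guidelines over a 18-month period". A secondary objective is "To determine the impact of the application on the quality of life of CKD patients". The title and the closing sentence of Section 1 also speak of effectiveness.

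**Design.** Section 3 states: "This is an observational, prospective cohort study". Eligibility in Section 4 includes "Owns a smartphone and is capable of using mobile applications", and the last step of the baseline visit in Section 5 is "Assist participant in downloading and setting up the smartphone application". No group without the app, staggered introduction, external comparator or series of measurements before the app is described. Follow-up assessments are at 3, 6, 9 and 12 months.

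**Outcome and test.** The primary outcome in Section 6 is adherence, "measured by changes in adherence scores from baseline to 12 months in the variables specified above", covering recommended medications and lifestyle. Besides descriptive statistics, Section 7 lists one method: "Paired t-tests or Wilcoxon signed-rank tests to compare baseline and follow-up measurements". App usage such as "Number of logins per week" is collected, but no analysis linking it to adherence is stated.

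**The concern.** The words effectiveness, enhancing and impact attribute change to the app. The planned test asks a different question: whether the average within-patient change is zero. With everyone given the app, that change is the sum of the app's effect and whatever else moved adherence over the same months.

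The protocol itself points to two such sources. The outcome is uptake of a guideline dated 2024, scored partly on prescription of named drug classes, and prescribing can change without an app. Patients are also assessed every three months for blood pressure, kidney function and guideline adherence, from the same starting point as the app.

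At stake is the main conclusion. If the plan is followed exactly, any background rise in adherence is credited to the app, and Section 9 commits the results to journals, conferences and the participants themselves.

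**Working it through.** **1. What the test estimates.** Write the mean change from baseline to 12 months as

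mean change = app effect + background trend + effect of study assessment.

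The paired t-test takes mean change = 0 as its null hypothesis (the signed-rank test has the matching null on the location of the changes). Separating the three terms needs patients without the app, or at least measurements before it. The protocol describes neither, so only the sum can be estimated.

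**2. Inputs for an illustration.** The protocol states no sample size, alpha, SD, effect size or background trend, so there is no figure of its own to reproduce. Everything in this step is assumed: two-sided alpha 0.05, zero app effect, n patients with paired data, and a background drift of d, in SDs of the within-patient change score.

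**3. Formula.** The paired t statistic follows a noncentral t distribution with n − 1 degrees of freedom and noncentrality d × √n. The probability of significance is the chance that it falls outside the two-sided 5% critical values.

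For n = 200, √200 = 14.14, so the noncentrality is 1.41, 2.83 and 4.24 for d = 0.1, 0.2 and 0.3. The probabilities are 0.29, 0.80 and 0.99.

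| Assumed n | d = 0 | d = 0.1 | d = 0.2 | d = 0.3 |
|---|---|---|---|---|
| 50 | 0.05 | 0.11 | 0.28 | 0.55 |
| 100 | 0.05 | 0.17 | 0.51 | 0.84 |
| 200 | 0.05 | 0.29 | 0.80 | 0.99 |
| 500 | 0.05 | 0.61 | 0.99 | >0.99 |

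The probability rises with n, so recruiting more patients does not help.

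**4. What a comparator would do.** The same drift was simulated in two equal groups (4,000 runs; total n = 100, 200 and 500; d = 0.1 to 0.3), comparing change scores with a two-sample t-test. With zero app effect the rejection rate stayed between 0.044 and 0.054. The drift cancels because both groups share it.

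**5. Quality of life.** Section 5 lists the questionnaire only under follow-up visits. As written there is no baseline value to pair, so the impact objective lacks even the before-after contrast.

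**The case against.** **The test is not wrong for its outcome.** A paired test fits a declared outcome of change from baseline, and it suits the secondary objective on changes in clinical parameters. This stands. The fault is causal wording on an uncontrolled design, not the choice of test.

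**The percentages are an ordinary power curve.** If adherence really drifts, the no-change hypothesis is false and the test is right to reject it. This stands too. The figures do not show a miscalibrated test. They show how often a correct rejection would be misread as an app effect.

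**The three-monthly assessments may be routine care.** The protocol does not say whether they are extra to usual visits. If they are routine, they add little. This source of change is therefore possible, not shown.

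**An unseen SAP may deal with it.** It could limit the interpretation, but it cannot supply a comparator or pre-app series that the protocol does not collect. Relating usage to adherence would not settle the matter either, since heavier users may simply be more motivated.

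**Stronger readings that the document does not support.** A reader might infer that regression to the mean inflates the change. That requires selection on extreme values, and Section 4 sets no threshold on blood pressure, eGFR, ACR or adherence; one noisy reading does not by itself bias a group mean change. A reader might also infer that a useless app is bound to look effective if prescribing is rising. At a drift of 0.1 SD the probability is only 17% with n = 100 and 29% with n = 200. Nor does the protocol show that a background rise exists or how large it is.

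**Conclusion.** The point holds as a mismatch between the stated aims and what the design can show. A significant paired test would establish that adherence changed among patients given the app. It would not answer the primary objective as worded, because background uptake and any effect of study assessment cannot be separated from the app.

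This conclusion rests on the text alone. Its size does not: 29%, 80% and 99% apply only under the assumed n = 200, alpha 0.05, zero app effect and drifts of 0.1, 0.2 and 0.3 SD, and no drift can be read from the protocol.

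The observational label is a lesser matter, largely one of terminology. Since the study helps introduce the exposure at baseline, single-arm before-after describes the design more accurately.

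**What to change.** **Change to make.** Reword the title, Section 1, the Section 2 objectives and the planned conclusion so that the aim is change in guideline adherence, and in quality of life, among patients given the app. In Section 3, describe a single-arm before-after study. In Section 7, state that change will not be attributed to the app. The paired t-test or signed-rank test can then stay. For quality of life, a change aim also needs the questionnaire at baseline; otherwise that objective should describe levels during follow-up.

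**Cost.** The rewording changes no study procedure. The price is a more modest conclusion, plus one questionnaire at baseline if change in quality of life is to be reported.

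**If an effect claim is kept.** It needs a comparator followed on the same schedule, for example by randomised, cluster or stepped introduction of the app. That is a different and larger study. A segmented model using records from before enrolment would be at most supportive. It addresses only pre-existing trend in record-based items, leaves out the lifestyle part of the primary outcome, and still credits the app with the start of study assessment and any switch from routine to protocol measurement. It also assumes that usable records exist and can be linked to data that Section 7 says are anonymised. Finally, it needs a clear start date for app use, which is uncertain because Section 8 takes consent through the app while Section 5 sets the app up last.

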- **Month 0:** Study initiation and baseline assessments.
- **Months 3, 6, 9:** Follow-up assessments.
- **Month 12:** Final follow-up assessments and data analysis.
- **Months 13-15:** Data analysis and manuscript preparation.
- **Month 16:** Dissemination of results.

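### The paired tests named for the baseline-to-12-month primary outcome leave out every patient without a month-12 score and make no use of that patient's month 3, 6 and 9 scores, so the gain may be biased if dropout is related to change

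*Protocol*

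**What the plan says.** Section 3 describes the design: "This is an observational, prospective cohort study". No control or comparison group appears anywhere in the protocol.

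Section 5 sets the follow-up schedule, "Participants will be assessed at 3, 6, 9, and 12 months. At each visit", and lists an adherence assessment and a review of app use (for example "Number of logins per week") among the tasks of each follow-up visit.

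Section 6 gives the primary outcome as guideline adherence, "measured by changes in adherence scores from baseline to 12 months in the variables specified above".

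Section 7 offers descriptive statistics and one family of tests: "Paired t-tests or Wilcoxon signed-rank tests to compare baseline and follow-up measurements". It names no method that combines the visits and gives the app-use data no role in the analysis.

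Section 10 places the last visit at month 12 ("Final follow-up assessments and data analysis"), whereas section 3 states "Participants will be assessed at baseline and at intervals over 18 months" and section 2 also refers to 18 months. This review takes month 12 as the primary time point because section 6 does. The two durations must be reconciled.

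**The concern.** A paired t-test or signed-rank test works on one difference per patient. For the primary contrast that difference exists only for patients scored both at baseline and at month 12. A patient seen at months 3, 6 and 9 and then lost is removed entirely, although the protocol has scheduled and collected three post-baseline scores that say how the patient was doing.

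This matters more here than in a randomised trial. There is no between-arm contrast in which similar losses on both sides might partly cancel, so any selection among those who reach month 12 passes straight into the reported effect. In a study of an app it is plausible that patients who stop using it are both less likely to return and less likely to have improved. The completer mean would then describe the patients for whom the app worked and be read as the effect in everyone enrolled.

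**Working it through.** **Inputs.** The document supplies the test (section 7), the contrast (section 6) and the visits (section 5). It gives no sample size, dropout rate, effect size, standard deviation or significance level, so there is no stated figure to reproduce. Every number below other than the visit months is an assumption or follows from one.

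**Step 1: bias of the completer mean.** Let d be the share without a month-12 score, C the mean change in completers and D the mean change the others would have shown. The mean over all enrolled is (1 − d)C + dD, so

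bias = C − [(1 − d)C + dD] = d(C − D) = d × g,

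where g is the gap between the groups, in SDs of change.

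| d | g = 0 | g = 0.25 | g = 0.5 | g = 1 |
|---|---|---|---|---|
| 10% | 0 | 0.025 | 0.05 | 0.10 |
| 20% | 0 | 0.05 | 0.10 | 0.20 |
| 30% | 0 | 0.075 | 0.15 | 0.30 |
| 40% | 0 | 0.10 | 0.20 | 0.40 |

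The bias takes the sign of g, so it reverses if those who leave have done better.

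**Step 2: effect on the test.** Suppose the true mean change over all enrolled is zero, the test is two-sided at an assumed 5%, and N are enrolled. Then n = N(1 − d) pairs remain, and the normal-approximation rejection rate is Φ(dg√n − 1.96) + Φ(−dg√n − 1.96).

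- N = 100, d = 10%, g = 0.25: 5.6%.
- N = 200, d = 20%: n = 160. With g = 0.25, dg√n = 0.05 × 12.65 = 0.63 and the rate is 9.7%. With g = 0.5, dg√n = 1.26 and the rate is 24.4%.
- N = 500, d = 20%: 17.0% (g = 0.25) and 51.6% (g = 0.5).

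A larger study makes this worse, because the bias stays fixed while the standard error shrinks.

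**Step 3: do the interim scores help?** Simulation of 400,000 patients with five visits, correlation 0.6 between any two visits, a gain rising linearly to 0.30 score-SD at month 12, and dropout after each visit depending on the change last observed. The comparison method predicts missing scores by sequential regression on baseline and the earlier visits. It is valid if data are missing at random, as a likelihood-based repeated-measures model is.

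| Who leaves (assumed) | Without month 12 | Completer paired change | Using months 3, 6, 9 |
|---|---|---|---|
| Poorer change, strong dependence | 20%; 38% | 0.41; 0.50 | 0.30; 0.30 |
| Poorer change, moderate dependence | 13%; 31% | 0.34; 0.39 | 0.30; 0.30 |
| Unrelated to change | 12%; 28% | 0.30; 0.30 | 0.30; 0.30 |
| Better change | 16%; 36% | 0.25; 0.18 | 0.30; 0.30 |

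The last column recovers the truth because dropout was made to depend only on observed scores. It shows what the scheduled visits can repair under that condition, not that they repair every form of dropout.

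**The case against.** The strongest reply is that the protocol says nothing about how many patients will leave or which ones. That is right. A reader might infer that the reported gain is bound to be too high, but the document supports only a conditional risk: the bias is zero if dropout is unrelated to change and runs the other way if improvers leave.

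A second reply is that section 7 does not tie its follow-up values to one visit, so a paired test at each of months 3, 6 and 9 fits its wording. It would therefore go too far to say that those visits are ignored altogether. What stands is narrower: such tests are separate comparisons on separate sets of attenders, and none of them feeds the month-12 estimate.

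A third is that missing-data handling belongs in an analysis plan, which may exist. The silence on missing data is indeed no finding. The test, however, is the protocol's own choice, and a plan that applies it as written to the stated primary outcome inherits the exclusion.

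Four further inferences are tempting and should not be drawn.

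- **Non-attenders are deleted instead of being scored as non-adherent.** Section 5 lists "Attendance at medical appointments" under adherence, but section 6 confines the primary outcome to medications and lifestyle. Whether attendance enters the primary score is unclear, and the appointments are not said to be the study visits.
- **Standard errors are too small because patients share doctors.** A stable doctor effect is in both values and cancels in the difference. Only variation between doctors in the change itself would matter, and the protocol gives no basis for its size.
- **Skewed ACR defeats the analysis.** The signed-rank test is already offered and meets much of this.
- **Missing scores could be filled from hospital records.** Nothing in the document establishes such access.

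**Conclusion.** The point holds as a conditional risk of bias in the primary estimate. It is certain from sections 6 and 7 that a paired test of the baseline-to-month-12 change excludes patients without a month-12 score and makes no use of their interim scores. The direction and size are not known.

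Under the assumed inputs, a true gain of 0.30 SD appears as 0.34 to 0.50 SD among completers when poorer responders leave, an excess of 0.04 to 0.20 SD. It appears as 0.30 SD when dropout is unrelated to change, and as 0.18 to 0.25 SD when improvers leave. These figures illustrate the mechanism and do not forecast this study. Because the interim scores are scheduled anyway and a standard method uses them, the change should be made.

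**What to change.** Make the primary analysis in section 7 a repeated-measures model on all enrolled participants, using all scores at 0, 3, 6, 9 and 12 months. If the adherence score is treated as continuous, this is a mixed model with visit as a factor and an unstructured covariance. If components are binary, use a suitable generalised model that remains valid when data are missing at random. State month 12 minus baseline as the primary contrast.

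Add a sensitivity analysis for data missing not at random, for example by assuming progressively worse scores after dropout than the model predicts. Keep the paired t or signed-rank test as a supportive analysis of completers, and report how many patients it excludes. Reconcile the 12- and 18-month statements so that the primary time point is not in doubt.

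The cost is small: some wording, slightly more programming and no new visits. With complete continuous data, the model's contrast equals the paired mean change. The model does rely on a missing-at-random assumption, which is why the sensitivity analysis is needed. The sponsor should also accept that the reported gain may become less favourable.

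### The named paired tests make no allowance for possible clustering of change by prescribing doctor, so standard errors may be too small

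*Protocol*

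**What the plan says.** Protocol section 7, under Statistical Analysis, has two bullets. One is descriptive; the other reads "Paired t-tests or Wilcoxon signed-rank tests to compare baseline and follow-up measurements". No term for doctor, clinic or site appears.

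The primary outcome in section 6 is guideline adherence, "measured by changes in adherence scores from baseline to 12 months in the variables specified above (recommended medications and lifestyle modifications"). Among the adherence items assessed at follow-up (section 5, item 3), the first is disease-modifying drug "prescription including ACE inhibitors and ARBs, SGLT2 inhibitors, GLP-1 analogues, Finerenone and endothelial antagonists". Blood pressure control, diet, physical activity and attendance follow.

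Section 1 describes the app as "designed to assist doctors and patients in following the 2024 KDIGO CKD guidelines". Section 3 states the design: "This is an observational, prospective cohort study". On setting, section 8 says only "The study protocol has been approved by the hospital ethics committee".

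The protocol does not state the sample size, the significance level, the number of doctors or sites, or the number of participants per doctor. The baseline and follow-up data lists in section 5 do not include the treating doctor.

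**The concern.** The paired t-test and the signed-rank test both take the within-patient changes as independent. Prescription is a prescriber's act, and part of the app's intended effect runs through doctors. If one doctor takes up the guideline and another does not, patients of the same doctor tend to change together. That correlation would come from the very mechanism the study is examining.

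Pairing helps only in part. It removes stable differences between doctors, such as one who has always prescribed more. It does not remove differences between doctors in how much they change.

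At stake is the precision claimed for the primary result. Under clustering of change, the confidence interval is too narrow and the test rejects too often. A strong response from a few prescribers could then look like firmer evidence for the app than it is.

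**Working it through.** The protocol states no sample size, power or significance level, so there is no figure of its own to reproduce. What follows is an illustration under stated assumptions.

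**Inputs from the protocol.** Patient-level paired tests (section 7); prescription within the primary outcome (sections 5 and 6); doctors among the app's intended users (section 1).

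**Inputs assumed.** A two-sided 5% test; m participants per doctor, from 5 to 40; ICC of the change score from 0.01 to 0.10. The no-clustering cases (m = 1, or ICC = 0) are included as a reference.

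**Formulas.**
- Design effect: DE = 1 + (m − 1) × ICC.
- Factor by which the standard error is understated: √DE.
- True two-sided error of a nominal 5% test: 2 × [1 − Φ(1.96/√DE)].

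**Three cases worked through.**
- m = 5, ICC = 0.01: DE = 1 + 4 × 0.01 = 1.04; √DE = 1.02; 1.96/1.02 = 1.92; true error 5.5%.
- m = 20, ICC = 0.05: DE = 1 + 19 × 0.05 = 1.95; √DE = 1.40; 1.96/1.396 = 1.40; true error 16%.
- m = 40, ICC = 0.10: DE = 1 + 39 × 0.10 = 4.9; √DE = 2.21; 1.96/2.214 = 0.885; true error 38%.

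**True error of a nominal 5% test.**

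| Participants per doctor | ICC 0 | ICC 0.01 | ICC 0.05 | ICC 0.10 |
|---|---|---|---|---|
| 1 | 5.0% | 5.0% | 5.0% | 5.0% |
| 5 | 5.0% | 5.5% | 7.4% | 9.8% |
| 10 | 5.0% | 6.1% | 10.4% | 15.5% |
| 20 | 5.0% | 7.2% | 16.1% | 25.0% |
| 40 | 5.0% | 9.6% | 25.4% | 37.6% |

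**Check by simulation** (paired t-test, no true mean change, 10,000 runs each):
- 10 doctors × 20 patients, stable doctor differences only: 4.6% rejections, so no inflation.
- 10 doctors × 20 patients, ICC of change 0.05: 16.4%, against 16.1% from the formula.
- 20 doctors × 10 patients, ICC of change 0.05: 10.1%, against 10.4%.

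The simulations confirm both the formula and the distinction it rests on: only variation between doctors in change matters. The layouts are illustrative and do not come from the protocol.

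**The case against.** The strongest reply is that the protocol does not show that the problem exists. A reader might infer that each doctor treats many participants and that the standard errors are therefore too small. The document supports neither step. It gives no count of doctors or of participants per doctor, and the ICC of change is unknown and could be zero. This stands: the point is conditional, and the range runs from negligible to severe according to what is assumed.

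Delivery as described is to individual patients. The app is set up with each participant, usage and feedback are reviewed at participant follow-up visits, and no doctor is enrolled or measured. Diet, activity and attendance depend largely on the patient, so a combined adherence score may have a lower ICC than its medication part. This also stands, and is a reason to look at the medication component in particular.

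If the conclusion is meant only for the participating doctors, taken as fixed, the inflation argument weakens. The protocol does not say which target is meant. Its general aim of assessing the app's effectiveness suggests something wider, but does not settle it.

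Finally, random effects and degrees of freedom are commonly left to an SAP, and one may exist. That is fair for the model details. But the protocol does not stay silent: it names a family of tests without a doctor term. The data lists also matter now, because an SAP cannot adjust for a prescriber who was never recorded.

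**Conclusion.** The concern holds in conditional form, as a cheap improvement. The protocol's own text supplies a plausible route to correlated change within doctors, and the tests it names make no allowance for it. If change clusters positively and doctors have more than one participant each, the direction is clear: standard errors too small and more false positives than nominal.

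The size cannot be computed from the document. Under 5 to 40 participants per doctor, an ICC of change of 0.01 to 0.10 and a two-sided 5% test, the true error is about 5.5% to 38%. With an ICC of 0 or one participant per doctor it stays at 5%. It would be wrong to read this as showing that the planned test is invalid in this study.

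**What to change.** Add a coded main prescriber, or clinic team where there is no single prescriber, to the baseline data. Reword section 7 so that the patient-level change in adherence, at least its medication component, is analysed with a mixed model that has a doctor random effect on change and small-sample degrees of freedom. Report the estimated ICC. With no clustering, this gives essentially the paired t-test.

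If too few doctors take part to estimate the doctor effect, show results by doctor, limit the conclusion to those doctors and state the limitation.

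A t-test on doctor-level means should not be the default. It weights doctors equally, which can change the quantity being estimated, and it has very few degrees of freedom when doctors are few: with three doctors, 2 degrees of freedom and a critical value of 4.30.

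The cost is one data field, a change of wording and wider intervals if clustering is present. The change does nothing about the lack of a described comparison group, which is a separate limit on attributing any improvement to the app.
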